7.4.2 Sensitivity analysis, subgroup analysis, exploratory analysis of the primary endpoint

7.5 SECONDARY ENDPOINTS

7.5.1 Key secondary endpoint

There are no key secondary endpoints defined for this trial.

7.5.1.1 Primary analysis of the key secondary endpoint

7.5.1.2 Sensitivity analysis, subgroup analysis, exploratory analysis of the key secondary endpoint

7.5.2 (Other) Secondary endpoints

Analysis of all secondary endpoints will be performed using the ITT and PPS populations.

Proprietary confidential information © 2020 Boehringer Ingelheim International GmbH or one or more of its affiliated companies

Pairwise comparisons of the *observed* proportions of patients at each dose level to placebo will be performed for the secondary endpoints. Confidence intervals will be calculated using the Newcombe method. P-values from Barnard tests of association will be displayed.

Pairwise comparisons of the *observed* proportions of patients at each dose level to placebo who are CRRs *at week 26* will be stratified *by race* (Asian vs. non-Asian) as a sensitivity analysis. Confidence intervals will be calculated using the Newcombe method. P-values from Barnard tests of association will be displayed. This same analysis will be performed for *observed* placebo-adjusted proportions of patients at each dose stratified *by proteinuria at screening* (UP/UC < 3 vs. UP/UC ≥ 3) as per the lab results.

7.7 EXTENT OF EXPOSURE

Duration of time on treatment will be derived for each patient & summarized by treatment group.

7.8 SAFETY ANALYSIS

All safety analyses will be performed on the treated set and performed in accordance with BI standards. Tabulations of frequencies/proportions will be used for the evaluation of categorical (qualitative) data, and tabulations of descriptive statistics will be used to analyse continuous (quantitative) data.

The format of the listings and tables will follow the BI guideline ‘Reporting of clinical trials and project summaries’ (6).

The individual values of all subjects will be listed, sorted by treatment, subject number and visit. The listings will be contained in Appendix 16.2.

7.8.1 Adverse events

AEs will be analysed using BI standards, as described in the guideline, ‘Handling and summarization of adverse event data for clinical trial reports and integrated summaries’ (7).

Unless otherwise specified, the analyses of adverse events will be descriptive in nature. All analyses of AEs will be based on the number of patients with AEs and NOT on the number of AEs.

The analysis of AEs will be based on the concept of treatment emergent AEs. This means that all AEs occurring between first drug intake and end of the residual effect period (REP) will be assigned to the randomised treatment. The residual effect period is defined as 50 days. All AEs occurring before first drug intake will be assigned to ‘Screening’ and all AEs occurring after last drug intake + 50 days will be assigned to ‘Follow-up’ (and presented in listings only). For details on the treatment definition, see [Section 6.1](#)

According to ICH E3 (8), in addition to Deaths and Serious Adverse Events, ‘other significant’ AEs need to be listed in the clinical trial report. These will be any non-serious adverse event that led to an action taken with study drug (e.g. discontinuation or dose reduced or interrupted).

An overall summary of adverse events will be presented. The frequency of patients with adverse events will be summarised by treatment, primary system organ class and preferred term. Separate tables will be provided for patients with adverse events leading to treatment discontinuation, other significant adverse events according to ICH E3 (8), related adverse events and serious adverse events. AEs will also be summarised by maximum RCTC grade.

Proprietary confidential information © 2020 Boehringer Ingelheim International GmbH or one or more of its affiliated companies

Adverse events of special interest (AESI) will be presented in tables and listings for the following:

- Injection site reactions and hypersensitivity, including anaphylaxis reaction
- Malignancies, lymphoproliferative disorders
- Severe infections and opportunistic infections
- Thromboembolism (Thrombosis and adjunct immunosuppression)
- Cytokine release syndrome
- Drug induced liver injury (DILI) (if applicable)

The system organ classes will be sorted by frequency, PTs will be sorted by frequency (within SOC).

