5.3.6 Adverse event collection and reporting

AE Collection

The following must be collected and documented on the appropriate eCRF by the Investigator:

- From signing the informed consent onwards through the Residual Effect period (REP), until trial completion, all AEs (serious and non-serious), and all AESIs.

[figure not shown]

Figure 5.3.6:1 AE collection

The REP is defined as 50 days after the last trial medication application. All AEs which occurred through the treatment phase and throughout the REP will be considered as on treatment please see [section 7.3.4](#). Events which occurred after the REP will be considered as post treatment events.

After the last per protocol contact the Investigator does not need to actively monitor patients for AEs. However, if the Investigator becomes aware of SAEs or AESIs that occurred after the last per protocol contact, the SAEs and AESIs should be reported by the Investigator to the Sponsor if considered relevant by the Investigator.

AE reporting to sponsor and timelines

The Investigator must report SAEs, AESIs, and non-serious AEs which are relevant for the reported SAE or AESI, on the BI SAE form via fax immediately (within 24 hours) to the Sponsor's unique entry point (country specific contact details will be provided in the ISF). In specific occasions the Investigator could inform the Sponsor upfront via telephone. This does not replace the requirement to complete and fax the BI SAE form.

For Japan: All SAEs and AESIs must be reported immediately to the head of the trial site. With receipt of any further information to these events, a follow-up SAE form has to be

provided. For follow-up information the same rules and timeline apply as for initial information.

Information required

For each AE, the Investigator should provide the information requested on the appropriate (e)CRF pages and the BI SAE form, e.g. onset, end date, intensity, treatment required, outcome, seriousness, and action taken with the investigational drug(s). The Investigator should determine the causal relationship to the trial medication, and any possible interactions between the investigational drug and a Non-Investigational Medicinal Product.

The following should also be recorded as an (S)AE in the (e)CRF and SAE form (if applicable):

- Worsening of the underlying disease or of other pre-existing conditions

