7.3.4 Safety analyses

All treated patients will be included in the safety analysis. In general, safety analyses will be descriptive in nature and will be based on BI standards. No hypothesis testing is planned.

Adverse events will be coded using the Medical Dictionary for Regulatory Activities (MedDRA) coding dictionary. Standard BI summary tables and listings will be produced. All adverse events with an onset between start of treatment and end of the residual effect period (REP), a period of 50 days after the last dose of trial medication, will be assigned to the treatment period for evaluation. Analysis will be performed based on randomised treatment.

Statistical analysis and reporting of adverse events will concentrate on treatment-emergent adverse events. To this end, all adverse events occurring between start of treatment and end of the residual effect period will be considered 'treatment-emergent'. The residual effect period is defined as 50 days. Adverse events that start before first drug intake and deteriorate under treatment will also be considered as 'treatment-emergent'.

Frequency, severity, and causal relationship of adverse events will be tabulated by system organ class and preferred term after coding according to the current version of the Medical Dictionary for Drug Regulatory Activities (MedDRA).

Laboratory data will be analysed both quantitatively as well as qualitatively. The latter will be done via comparison of laboratory data to their reference ranges. Values outside the reference range as well as values defined as clinically relevant will be highlighted in the

listings. Treatment groups will be compared descriptively with regard to distribution parameters as well as with regard to frequency and percentage of patients with abnormal values or clinically relevant abnormal values.

Vital signs, physical examinations, or other safety-relevant data observed at screening, baseline, during the course of the trial and at the end-of-trial evaluation will be assessed with regard to possible changes compared to findings before start of treatment.

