6. GENERAL ANALYSIS DEFINITIONS

6.1 TREATMENTS

For reporting purposes, all randomised patients will be classified into one of the following treatment groups:

Sort order	Treatment	Long label	Short label
01	B	BI 655064 120mg	BI 120mg
02	C	BI 655064 180mg	BI 180mg
03	D	BI 655064 240mg	BI 240mg
04	A	Placebo	Placebo

These will be the default labels and sort order for reporting the treatment groups.

The following study periods based on actual start and stop dates of study treatment administration are defined:

Screening: day of informed consent to day prior to the start of randomised medication

Treatment: start date of randomised double-blind medication to date of last dose

Follow-up: day after the last dose of randomised double-blind medication through trial completion and after trial completion

Rules for assigning AEs/laboratory data to the study periods are as follows.

AEs/laboratory data will be assigned to the treatment period if they occur/samples were taken after the first injection of study medication to the date of last administration of study medication plus 50 days.

Since AE onset time was not recorded, investigators were asked to provide more information for AEs with date of onset equal to date of first injection. Additional information was to be provided in the AE comment field. The trial team will review the comments & will impute a time to capture onset as prior to or following first injection of study medication. An analysis data set will be created to incorporate this information. If the site indicates that the AE onset time is prior to trial medication administration then the AE will be assigned to the screening period. If the site indicates that the AE onset time is after trial medication administration or there is no information regarding onset then the AE will be assigned to the treatment period.

Adverse events with onset on or after the 51st day after the last administration of trial medication will be considered 'Follow-up' events. However, if the patient rolls over to the extension trial (1293.13) & receives the first dose of trial medication in 1293.13, any new events or worsening of existing events will be assigned to the treatment period of 1293.13.

Laboratory data on or after the 51st day after the last administration of trial medication will be considered 'Follow-up' data.

Proprietary confidential information © 2020 Boehringer Ingelheim International GmbH or one or more of its affiliated companies

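### The SAP assigns all adverse events with onset before first dose to Screening and omits, undeclared, the protocol rule that those deteriorating on treatment are treatment-emergent

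*SAP*

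**What the plan says.** Protocol 7.3.4 builds its definition in two parts. The first is a time window: "all adverse events occurring between start of treatment and end of the residual effect period will be considered" treatment-emergent. The second extends it: "Adverse events that start before first drug intake and deteriorate under treatment will also be considered as" treatment-emergent.

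SAP 7.8.1 keeps the window, with the same length ("The residual effect period is defined as 50 days"), but replaces the extension with a flat rule: "All AEs occurring before first drug intake will be assigned to" Screening. SAP 6.1 also assigns AEs to the treatment period by when they occur. For events dated on the day of first injection, it says: "If the site indicates that the AE onset time is prior to trial medication administration then the AE will be assigned to the screening period".

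The SAP mentions worsening of an AE in one place only, SAP 6.1, for patients who enter the extension trial and take their first dose there: "any new events or worsening of existing events will be assigned to the treatment period of 1293.13".

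SAP section 4 lists the changes to the planned analysis. They concern the renal response derivations, protocol deviations and analysis populations, and the logistic regression covariates. It does not mention the AE definition. SAP section 3 says that the SAP builds on section 7 of the protocol, which contains the deterioration rule.

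**The concern.** The two documents give different answers for the same event. Protocol 5.3.6 collects AEs "From signing the informed consent onwards through the Residual Effect period (REP), until trial completion, all AEs (serious and non-serious), and all AESIs", and protocol 6.2.1 places the screening visit 7 to 28 days before randomisation. There is therefore a period in which AEs can be opened before first dose. Protocol 3.2 and 6.2.2 expect some patients to have started mycophenolate and steroids by then, so such events are plausible.

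BI 655064 is an immunosuppressant, and an event that was mild at first dose and becomes severe on drug is one a safety table should show. SAP 7.8.1 bases its AE analysis on treatment-emergent events. The system organ class and preferred term, maximum RCTC grade, serious-event and special-interest summaries would then miss it. Protocol 7.1 makes safety part of the dose decision, and any error of this kind is in the direction of under-counting harm.

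**Working it through.** The plan gives no figure to reproduce, so the check is to run each type of event through both sets of rules.

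- **Onset from first dose to last dose + 50 days.** Protocol: treatment-emergent. SAP: treatment period. They agree.
- **Onset before first dose, no deterioration.** Protocol: not treatment-emergent. SAP: Screening. They agree.
- **Onset before first dose, deterioration on treatment entered as a new AE with its own on-treatment onset date.** Protocol: treatment-emergent. SAP: the new record falls in the treatment window. They agree.
- **Onset before first dose, deterioration on treatment kept under the original AE record.** Protocol: treatment-emergent. SAP: Screening. They disagree.

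The conflict is thus confined to the fourth type. Whether it occurs depends on two things.

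1. *How sites record worsening.* Protocol 5.3.6 asks for worsening of the disease or of other pre-existing conditions to be recorded as an AE. Protocol 5.3.1 and 5.3.2 ask the same for baseline conditions found worse at later examinations. Protocol 5.3.6 ties baseline conditions to abnormalities present before trial inclusion. No text tells sites to open a new record when an AE first reported after consent gets worse.
2. *Whether the sponsor's AE-handling guideline, cited in SAP 7.8.1, has a worsening rule.* It was not supplied.

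Neither document gives the number of AEs opened before first dose or the share that worsen, so no expected count can be derived. The weight of a single patient follows from the planned arm sizes:

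- 120 mg and 180 mg arms: 1/20 = 0.050, or 5 percentage points.
- 240 mg and placebo arms: 1/40 = 0.025, or 2.5 percentage points.

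These are upper limits per patient. SAP 7.8.1 counts patients, not events, so a patient who already has another treatment-emergent event in the same table row changes nothing in that row.

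**The case against.** The best defence is that the SAP omits the rule without revoking it. The SAP rests on protocol section 7, defers to a sponsor guideline for AEs, and lists no change, which also fits no change being intended. Worsening of a pre-existing condition is a reportable AE, and an event already present at first dose could be read as pre-existing. Exclusion criterion 10 bars clinically important infections, which narrows the most obvious example. Worsening cytopenias would also appear in the laboratory analyses of SAP 7.8.2 whatever the AE dating.

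Much of this stands as a limit on the consequence. A reader might infer that deteriorations on drug necessarily drop out of the safety tables. The documents do not support that, because loss requires both that the worsening stay under the pre-dose record and that the guideline be silent. A reader might also want a number of lost patients, but any such figure would rest on assumed rates. Two SAP sentences should not be over-read. The day-of-injection rule covers only onsets on that day, and the roll-over sentence divides events between two trials. The latter does show that the sponsor can assign a worsening to a different period from the event itself. The listings-only remark in SAP 7.8.1 is attached to Follow-up events, and the SAP does not say how Screening events are displayed.

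The defence does not remove the conflict. The flat wording of SAP 7.8.1 leaves no room for the exception, and SAP 6.1, to which it refers for details, has none. Protocol 7.3.4 also invokes the sponsor's standards and still states the rule, alongside the recording instructions in the same protocol. Its authors did not treat either as making it unnecessary.

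**Conclusion.** The point holds as an undeclared departure of the SAP from the protocol's definition of a treatment-emergent event. A programmer following SAP 6.1 and 7.8.1 literally would classify some events differently from protocol 7.3.4. The practical effect is conditional. It reaches only AEs opened between consent and first dose that deteriorate on treatment under a single record, and only if the sponsor guideline does not already cover them. The number of such events is unknown and may be small. Each affected patient moves an event rate by at most 5 points in the 20-patient arms and 2.5 points in the 40-patient arms. It should be corrected because it concerns safety, can only lower treatment-emergent counts, and is cheap to put right.

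**What to change.** Restore the protocol 7.3.4 rule in SAP 6.1 and 7.8.1. An AE with onset before first dose that deteriorates between first dose and last dose + 50 days is treatment-emergent, and Screening is kept for pre-dose AEs that do not deteriorate. The SAP should also say how deterioration is identified from the data, since the protocol does not define the word. If the sponsor meant to drop the rule, SAP section 4 should list the change and give the reason.

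The cost is a short text change and a derivation flag. The flag depends on how the eCRF records worsening within an AE. The examples of AE data in protocol 5.3.6 include onset, end date and intensity but no date of worsening, so it should first be checked that the flag can be derived. Treatment-emergent counts may rise slightly.

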3. PK samples will be collected before study medication administration on these days if the visit date coincides with a day of injection; therefore study medication should be administered on site in that case. If the visit does not correspond to an injection day, the PK sample will be taken at anytime during the visit. Exact date and time of sampling should be recorded. See [Section 5.4](#)
4. Oral glucocorticoids have to be started on day 4 (or day 1 if IV steroids were already received) and tapered to 10mg prednisone equivalent within 12 weeks.
5. Starting from week 2, patients have to administer the injections with BI 655064/placebo by themselves always 7 days after the previous dose.
6. Safety lab tests : details of tests is given in [section 5.3.3](#)
7. Pregnancy test will be performed in women of childbearing potential every 4 weeks. A serum pregnancy test will be performed at screening visit. Urine dipstick tests will be done during the screening phase (8-10 days after the first test) and immediately before starting medication. It will be repeated at visits every 4 weeks and will be provided for at home pregnancy testing as soon as visit intervals are > 4 weeks,. In case of a positive urine pregnancy test result, a blood sample for serum pregnancy test will be drawn for confirmation. Only those females with a negative pregnancy test will receive study medication and will be allowed to start treatment with MMF
8. Will be measured in serum and urine
9. Questionnaires should be completed in the following order: LupusPRO, SF-36, FACIT-F, before any other visit assessment
10. EOT visit has to be carried-out for all patients when they stop treatment. At week 52, patients who reach at least partial response (based on values obtained at week 46) will be offered to enter a maintenance trial (trial 1293.13). Patients who stopped treatment before week 52 will not be allowed to participate in the maintenance trial.
11. Follow up visits to be performed after end of treatment except for patients entering the maintenance trial 1293.13 and patients who have withdrawn drug prematurely
12. For randomized patients leaving the study before the planned EOS, their vital status should be collected at week 60

TABLE OF CONTENTS

TITLE PAGE	1
CLINICAL TRIAL PROTOCOL SYNOPSIS	2
FLOW CHART	5
TABLE OF CONTENTS	9
ABBREVIATIONS	12
1. INTRODUCTION.....	15
1.1 MEDICAL BACKGROUND	15
1.2 DRUG PROFILE	16
2. RATIONALE, OBJECTIVES, AND BENEFIT - RISK ASSESSMENT	18

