5.3.5 Assessment of adverse events

5.3.5.1 Definitions of AEs

Adverse event

An adverse event (AE) is defined as any untoward medical occurrence in a patient or clinical investigation subject administered a pharmaceutical product and which does not necessarily have to have a causal relationship with this treatment.

An AE can therefore be any unfavourable and unintended sign (including an abnormal laboratory finding), symptom, or disease temporally associated with the use of a medicinal product, whether or not considered related to the medicinal product.

Serious adverse event

A serious adverse event (SAE) is defined as any AE which:

- results in death,
- is life-threatening,
- requires inpatient hospitalisation or prolongation of existing hospitalisation,

- results in persistent or significant disability or incapacity,
- is a congenital anomaly/birth defect,
or
- is to be deemed serious for any other reason if it is an important medical event when based upon appropriate medical judgment which may jeopardize the patient and may require medical or surgical intervention to prevent one of the other outcomes listed in the above definitions.

Life-threatening in this context refers to an event in which the patient was at risk of death at the time of the event; it does not refer to an event that hypothetically might have caused death if more severe.

For Japan: The following events will be handled as “deemed serious for any other reason”. An AE which possibly leads to disability will be reported as an SAE.

Every new occurrence of cancer will be reported as a SAE regardless of the duration between discontinuation of the drug and the occurrence of the cancer.

AEs considered “Always Serious”

In accordance with the European Medicines Agency initiative on Important Medical Events, Boehringer Ingelheim has set up a list of AEs, which by their nature, can always be considered to be “serious” even though they may not have met the criteria of an SAE as given above.

The latest list of “Always Serious AEs” can be found in the RDC system. These events should always be reported as SAEs.

Adverse events of special interest (AESIs)

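### Deaths and malignancies more than 50 days after the last dose appear in listings only, and the week-60 vital status has no planned summary, so no by-arm count covers the full follow-up

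*SAP*

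**What the plan says.** SAP 7.8.1 bases the adverse-event analysis on treatment-emergent events: "The residual effect period is defined as 50 days". Events "after last drug intake + 50 days will be assigned to" follow-up "and presented in listings only". SAP 6.1 sets the same boundary: "Adverse events with onset on or after the 51st day after the last administration of trial medication will be considered" follow-up events. It makes one exception, for patients who enter extension trial 1293.13: new or worsening events after their first dose there belong to that trial.

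Within the window, SAP 7.8.1 plans event frequencies by treatment, a separate table of serious events, and tables and listings for events of special interest, including malignancy and lymphoproliferative disorders.

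The 50-day window comes from the protocol. Section 5.3.6 says: "Events which occurred after the REP will be considered as post treatment events". Section 7.3.4 uses the same 50 days and puts the emphasis of reporting on treatment-emergent events.

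The protocol collects data beyond that window. Section 3.3.4.1 stresses recording safety data to week 52 for patients who stop the drug early, and section 6.2.3.3 sets their visits, with adverse-event collection, up to week 52. Flow chart footnote 12 adds: "For randomized patients leaving the study before the planned EOS, their vital status should be collected at week 60". Section 6.2.3.3 likewise seeks vital status at the planned end-of-study visit when such a patient misses the visits.

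**The concern.** The trial adds an immunosuppressive antibody to mycophenolate and steroids, and protocol 5.3.5.1 names lymphoproliferative disease as a possible risk. Death and malignancy are the safety outcomes least naturally confined to 50 days after the last injection. Protocol 7.3 promises a descriptive comparison of safety between the three active arms and control.

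Under the SAP rule, a death or lymphoma found on day 51 or later after the last dose enters no count by arm. The time affected belongs mainly to patients who stop early, and section 3.3.4.1 gives adverse events and worsening disease among the reasons for stopping. If stopping differs between arms, so does the amount of follow-up that feeds the tables. The report could then show by-arm counts of deaths and cancers that omit events the trial deliberately collected. The week-60 vital status would inform no planned table.

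**Working it through.** The plan gives no figure to reproduce. The check is a reading of the text plus day arithmetic.

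**Inputs**
- Window after the last dose: 50 days (SAP 7.8.1; protocol 5.3.6 and 7.3.4).
- Calendar: day = 7 × week + 1. This reproduces the flow chart: week 52 = 7 × 52 + 1 = 365; week 60 = 7 × 60 + 1 = 421.
- Last planned injection: week 51 (protocol Table 4.1.4: 1), so day 7 × 51 + 1 = 358.
- End of scheduled adverse-event follow-up after stopping more than 8 weeks before week 52: week 52, day 365 (protocol 6.2.3.3).
- Vital status: week 60, day 421 (flow chart footnote 12).

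**Completers who do not roll over**
Window end = 358 + 50 = day 408. Listing-only time = 421 − 408 = 13 days, and 13/421 = 3%. With the ±5-day visit window the range is 8 to 18 days.

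**Early stoppers**
Window end = last-dose day + 50. The listing-only share is (365 − window end)/365 for adverse events and (421 − window end)/421 for vital status.

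| Last dose | Day | Window end | Adverse events to week 52 | Vital status to week 60 |
|---|---|---|---|---|
| Week 4 | 29 | 79 | 286/365 = 78% | 342/421 = 81% |
| Week 10 | 71 | 121 | 244/365 = 67% | 300/421 = 71% |
| Week 20 | 141 | 191 | 174/365 = 48% | 230/421 = 55% |
| Week 26 | 183 | 233 | 132/365 = 36% | 188/421 = 45% |

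The two columns need different end points. For all four stop weeks, section 6.2.3.3 requires no follow-up visits after week 52, so adverse events are actively collected to day 365 only. Only vital status reaches day 421.

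**What is tabulated by arm**
- Treatment plus 50 days: event frequencies by treatment; serious events, which include fatal ones because protocol 5.3.5.1 makes an event resulting in death serious; and malignancy and lymphoproliferative disorders as events of special interest.
- Later: nothing. Listings are sorted by treatment (SAP 7.8), so late events stay visible, but no count or denominator is planned.
- Vital status at week 60: no use in the available SAP text.

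**Scale of one event**
One uncounted death is 1/20 = 5 percentage points in a 20-patient arm and 1/40 = 2.5 points in a 40-patient arm. This is not a forecast: the documents give no expected rate of death, cancer or discontinuation.

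**The case against.** Three stronger readings are tempting, and the documents support none of them.

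- *A reader might infer that no by-arm comparison of deaths or malignancies is planned at all.* SAP 7.8.1 tabulates malignancy events of special interest and serious events, fatal ones included, within treatment plus 50 days.
- *A reader might infer that the protocol counts cancers without a time limit.* The sentence "Every new occurrence of cancer will be reported as a SAE regardless of the duration between discontinuation of the drug" is a reporting duty for sites, not an analysis rule. It follows a sentence specific to Japan, so its scope is unclear. Section 5.3.6 also ends active monitoring at the last per-protocol contact. The point does not depend on this sentence.
- *A reader might infer that the SAP contradicts the protocol.* Both use 50 days, and the protocol itself classes later events as post-treatment.

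The remaining case for leaving the plan alone has some force. This is an exploratory phase II trial with no safety hypothesis test. A data monitoring committee sees unblinded safety data during the trial. Listings sorted by treatment let a reader count a handful of late deaths by hand, and the sponsor's own standard for adverse-event summaries, which is not available here, may add a line for fatal events. A crude count to the end of study would also mix unequal follow-up, because patients who roll over skip the week-56 and week-60 visits.

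These arguments limit the point but do not remove it. Section 7.3.4 puts the emphasis on treatment-emergent events and does not bar a further table. The listings-only restriction is written in the SAP, not in the visible protocol text, and nothing available shows that a sponsor standard overrides it. The rollover objection bears on how the table is built, and the remedy must deal with it.

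**Conclusion.** The point holds in a limited form. Deaths and malignancies more than 50 days after the last dose are listed but not counted by arm, and the week-60 vital status has no planned summary. No by-arm all-cause death or malignancy summary over the full follow-up is therefore specified.

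The effect is negligible for completers and substantial for patients who stop in the first half of the treatment year. The shares assume nominal visit days, a last dose on the day of the stated week, and patients who stay in follow-up to week 52 or have vital status obtained at week 60. How much this matters overall depends on how many patients stop early and in which arms, which the documents do not state. The finding also rests on the available SAP text and assumes that no unseen sponsor standard adds a whole-study death table. It is a gap in presentation that is cheap to close. It is not an error in the 50-day rule.

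**What to change.** Add to SAP 7.8.1 a descriptive table by randomised arm, on the treated set and regardless of the 50-day window, showing:

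- (a) all deaths, including those known only from vital status, to week 60 or last contact;
- (b) malignancy and lymphoproliferative events of special interest, to last contact.

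Flag events after the residual effect period. For patients who roll over, end counting at the first dose in 1293.13, in line with SAP 6.1. Show the length of follow-up per arm beside the counts. Keep the 50-day rule for all other adverse-event tables.

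The cost is one or two tables from data already collected, with no change to visits, treatment or the efficacy analysis. There are two drawbacks. Some late events will follow other therapy, which the flag makes visible. Follow-up will differ between rollover and other patients, so the counts must be read with the follow-up lengths.
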